DLT assessment will occur in the initial 28 days (Cycle 1) of treatment for Cohorts 1 and 2. In the case of Cohort 3, DLT evaluation will be done in 32 days which includes the initial 4 days of the ramp-up phase. Safety and tolerability will be assessed by the incidence and severity of adverse events as determined by NCI Common Terminology Criteria for Adverse Events (NCI CTCAE v 5.0). A Safety Review Committee (SRC) comprised of the Medical Monitor(s), Principal Investigators, and Sponsor representatives will review safety information and decide upon dose escalation and further patient enrollment.

A DLT is defined as any of the following toxicities occurring during Cycle 1 during Part 1 (Single agent Dose Escalation Part) unless clearly or incontrovertibly related to the underlying malignancy, any other comorbidities or concomitant medications or extraneous causes:

The DLTs include:

- Decrease in Left Ventricular Ejection Fraction (LVEF) to < 50% **AND** an absolute drop in LVEF by > 10%.
(Note: Both need to be fulfilled to be called a DLT)
- Grade 3 or higher Left Ventricular Systolic Dysfunction.
- Asymptomatic Systolic BP ≥ 160 mmHg **AND/OR** Diastolic BP ≥ 100 mmHg, persisting for 3 days despite optimal medical management.
- Symptomatic Systolic BP ≥ 160 mmHg **AND/OR** Diastolic BP ≥ 100 mmHg, regardless of duration.
- Grade 4 hypertension.
- Myocardial Infarction, new onset angina, Transient Ischemic Attack (TIA), or Stroke.
- Asymptomatic Grade 3 or higher QTc prolongation (Average QTcF > 500 ms. and/or >60 ms. change from baseline).
- Grade 2 or higher QTc prolongation (Average QTcF: 481- 500 ms.) with cardiovascular symptoms suggestive of arrhythmia, such as palpitation, shortness of breath, chest pain, etc.

Note: If the QTcF interval exceeds 480 ms. at any timepoint, the ECG will be repeated twice, and the average reading will be recorded.

- Grade 3 or higher Sinus Bradycardia.
- Grade 2 or higher Atrial Fibrillation.
- Grade 2 or higher Atrial Flutter.
- Grade 2 or higher Ventricular Arrhythmia.

- Grade 2 or higher Atrio-Ventricular Block.
- Asymptomatic elevation of Cardiac Troponin I and/or Cardiac Troponin T $\geq 1.2 \times$ ULN confirmed by two separate readings.
- Grade 2 or higher Rhabdomyolysis.
- Grade 2 or higher CPK elevation ($2.5\text{-}5 \times$ ULN) with Grade 2 or higher muscle weakness, myalgia, or myopathy.
- Asymptomatic Grade 3 or higher CPK elevation ($> 5.0 \times$ ULN).

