This study may be prematurely terminated, if in the opinion of the Sponsor there is sufficiently reasonable cause. In the event of such action, written notification documenting the reason for the study termination will be provided to each Investigator and the regulators.

The study will be terminated if any of the following circumstances occurs:

- Occurrence of two DLTs at any dose level, without adequate PK exposure where de-escalation is not meaningful for further drug development.
- Determination of unexpected, significant, or unacceptable risk to subjects.
- Slow recruitment.
- Plans to modify, suspend, or discontinue the development of the study treatment.
- Decisions of regulatory authorities or IRB/IEC.

Enrolment in the study will be interrupted and engagement with regulators will immediately occur, if any of the following events (irrespective of the cycle) occur **at any time (during or beyond the DLT evaluation period)**:

- Any case of life-threatening or fatal cardiovascular toxicity, e.g., malignant hypertension, unstable angina, myocardial infarction, stroke, TIA (transient ischemic attack), ventricular arrhythmia, etc.
- Any case of life-threatening or fatal rhabdomyolysis
- Any other case of life-threatening or fatal event, which is not clearly or incontrovertibly related to the underlying

	
malignancy, any other co-morbidities or concomitant medications or extraneous causes.
 
 •  
In addition to above “Interruption Criterion” for the study, if there are non-life threatening cardiovascular / muscular DLT equivalents in patients, in the post- DLT period, then dosing in those patients will be stopped and all the safety data will be thoroughly evaluated as a whole. If such non-life threatening DLT equivalents (for cardiovascular and/or muscular toxicity) are occurring in more than 20% of patients at any specific dose or across dosages, then a report will be prepared and presented to the agency, for discussion if the study should be stopped or continued. If a DLT or DLT equivalent (cardiovascular and/or muscular toxicities) AEs are observed in over 30% of patients at a particular dose level or across multiple doses over any treatment duration, then the enrollment in the study will be halted. A comprehensive safety report will be prepared and presented to regulators to guide the decision-making process for the next steps for the trial.

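### Cycle 1 cardiovascular and muscular DLTs count toward the 30% enrolment halt but not toward the 20% agency report, which leaves a gap at a dose level expanded to about 18 patients

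*Protocol*

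**What the plan says.** All of this stands in the Protocol, section 1.0 Synopsis.

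- **Report rule** (Early termination or Interruption Criteria). The paragraph opens with its subject: "if there are non-life threatening cardiovascular / muscular DLT equivalents in patients, in the post- DLT period". The threshold follows: "If such non-life threatening DLT equivalents (for cardiovascular and/or muscular toxicity) are occurring in more than 20% of patients". It applies by dose or over all doses, and its consequence is a report to the agency to discuss whether the study goes on.
- **Halt rule** (next sentence). "If a DLT or DLT equivalent (cardiovascular and/or muscular toxicities) AEs are observed in over 30% of patients". This rule covers the whole time on treatment, again by dose or over several doses, and its consequence is that enrolment stops. The halt has its own report: "A comprehensive safety report will be prepared and presented to regulators to guide the decision-making process".
- **Meaning of DLT** (Dose-Limiting Toxicities). "A DLT is defined as any of the following toxicities occurring during Cycle 1". For Cohort 3 the evaluation window is 32 days, including the four ramp-up days.
- **Group sizes.** Six DLT-evaluable patients per cohort and about 18 over three cohorts. If a cohort shows acceptable safety, PK and PD, escalation stops and that cohort is enlarged to about 18 in total, including its first six (Rules for escalation and de-escalation).

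**The concern.** The two sentences stand next to each other, concern the same toxicity class and the same scope (one dose or several), and rise in threshold and consequence. A sponsor applying them would naturally treat the 20% rule as the lower step and the 30% rule as the upper one, but they count different patients. A patient with a non-life-threatening cardiac or muscular DLT in Cycle 1 enters the upper count and not the lower.

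At stake is the discussion with the agency while the rate lies between 20% and 30%. If part of that rate comes from Cycle 1, the lower rule can stay silent. Two people can also apply the text differently: one reads 'such' strictly and files nothing, the other counts every affected patient and files a report.

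**Working it through.** **1. Numerators side by side**

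| | 20% report | 30% halt |
|---|---|---|
| Toxicity | cardiovascular/muscular | cardiovascular/muscular (natural reading of the parenthesis) |
| Severity | non-life-threatening only | no limit stated |
| Period | after the DLT period | any treatment duration |
| Cycle 1 DLT counted? | no | yes |

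The plan gives no error rate or operating characteristic for either rule, so there is no figure to reproduce.

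**2. Smallest counts that exceed each threshold**

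| Patients | Over 20% | Over 30% |
|---|---|---|
| 6 | 2 (33.3%) | 2 (33.3%) |
| 18 | 4 (22.2%) | 6 (33.3%) |
| 24 | 5 (20.8%) | 8 (33.3%) |

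**3. Three completed cohorts of six.** Within a cohort, 1/6 = 16.7% exceeds neither threshold and 2/6 = 33.3% exceeds both. Pooled over 18, exceeding 20% needs at least 4 affected patients. Four patients in three cohorts put at least two in one cohort, which is already a halt at that dose, with its report. The probability of a pooled rate above 20% with neither report due is therefore 0.

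**4. One dose level expanded to 18.** Here 4 or 5 affected patients lie above 20% and below the halt. The report rule needs at least 4 late events, so it stays silent in these cases:

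- 4 affected, at least 1 of them in Cycle 1 (late count at most 3/18 = 16.7%);
- 5 affected, at least 2 of them in Cycle 1 (for example 2 + 3: 5/18 = 27.8% affected, 3/18 = 16.7% seen).

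If Cohort 1 is the expanded dose, the across-dose count is the same 18 patients. If Cohort 2 is expanded and Cohort 1 had no events, the across-dose late count is 3/24 = 12.5%, also silent.

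**5. How often.** Assumptions, since the protocol gives no rates: each patient is affected with probability r; an affected patient has one non-life-threatening event, in Cycle 1 with probability f and otherwise later; at most 1 of the first 6 is affected, because 2/6 would already exceed 30%. Let K be the number affected among 18. Then

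P(gap) = P(K=4)·[1 − (1−f)⁴] + P(K=5)·[1 − 5f(1−f)⁴ − (1−f)⁵],

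where P(K=k) = w₀·Bin(k; 12, r) + w₁·Bin(k−1; 12, r), and w₀, w₁ are the probabilities of 0 and 1 affected among the first 6, rescaled to sum to 1.

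*Low end, r = 0.15, f = 0.3.* w₀ = 0.377/0.776 = 0.486 and w₁ = 0.514. P(K=4) = 0.486 × 0.0683 + 0.514 × 0.1720 = 0.122. P(K=5) = 0.486 × 0.0193 + 0.514 × 0.0683 = 0.045. P(gap) = 0.122 × 0.760 + 0.045 × 0.472 = 0.11.

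*High end, r = 0.30, f = 0.7.* w₀ = 0.28 and w₁ = 0.72. P(K=4) = 0.28 × 0.2311 + 0.72 × 0.2397 = 0.237. P(K=5) = 0.28 × 0.1585 + 0.72 × 0.2311 = 0.211. P(gap) = 0.237 × 0.992 + 0.211 × 0.969 = 0.44.

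The same formula over the grid gives:

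| r | f = 0.3 | f = 0.5 | f = 0.7 |
|---|---|---|---|
| 0.15 | 0.11 | 0.15 | 0.16 |
| 0.20 | 0.20 | 0.27 | 0.29 |
| 0.25 | 0.26 | 0.36 | 0.39 |
| 0.30 | 0.28 | 0.39 | 0.44 |

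This describes the count at 18 patients. It does not model looks at intermediate numbers, where either rule might already have fired.

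**The case against.** The best defence is that the two rules do different jobs. The paragraph on the 20% rule is introduced as an addition to the single-case interruption rule and is about toxicity after the DLT period. Cycle 1 is already covered by Safety Review Committee review and the 2-of-6 rule. A late-toxicity rule plus an all-period cap is a coherent design, and nothing in the text says that the report must precede the halt. This stands in part: the sentences do not contradict each other, and calling the 20% rule a first step is an inference from their layout. But the committee consists of medical monitors, investigators and sponsor representatives, and neither it nor the 2-of-6 rule requires a report to the agency or adds Cycle 1 and later events together.

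Other safeguards also narrow the point. Any single life-threatening or fatal cardiovascular event or rhabdomyolysis, in any cycle, interrupts enrolment and brings in regulators at once. A late DLT equivalent prompts an overall safety evaluation whatever the percentage. What remains uncovered is non-life-threatening Cycle 1 events in a group large enough to separate the two thresholds.

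Three stronger readings are tempting and are not supported:

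- A reader might treat the planned 18 as one pool and infer a large chance of a missed report during escalation. Both rules also apply at each dose, and in three completed cohorts of six that chance is 0 (step 3).
- A reader might infer that a halt could leave regulators uninformed. With 3 Cycle 1 and 3 later events in an expanded cohort, 6/18 = 33.3% halts while the report rule reads 16.7%, but the halt carries its own safety report. Only the earlier discussion is missing.
- A reader might infer that the halt counts DLTs of every kind. The parenthesis most naturally limits both terms to cardiovascular and muscular toxicity.

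**Conclusion.** The point holds in a limited form. The report rule and the halt rule count different patients, and Cycle 1 cardiovascular and muscular DLTs enter only the second. With completed cohorts of six this has no consequence. At a dose level expanded to about 18, 4 or 5 affected patients (22.2% or 27.8%) can pass with no report due. The chance of this is about 11% to 44% under assumed event rates of 15% to 30% and 30% to 70% of events in Cycle 1, given at most 1 of the first 6 affected. The mismatch follows from the wording alone; its frequency rests on those assumed rates and is illustrative. The loss is an intermediate discussion with the agency, not the halt itself or the handling of life-threatening events. It is worth correcting because the expansion is already written into the protocol.

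**What to change.** Reconcile the two sentences so that both thresholds count the same patients: each patient with a cardiovascular or muscular DLT or DLT equivalent, in Cycle 1 or later, counted once. Leave the 20% and 30% thresholds and the rule on dosing in individual patients as they are. If the narrower 20% count is intended, say that it is a late-toxicity rule only and not a lower step before the halt. In the same edit, make plain that the parenthesis in the halt rule limits both DLTs and DLT equivalents, if that is meant.

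The cost is about one sentence in an amendment. With a common count the agency report may fall due earlier: at 18 patients, at the fourth affected patient whatever the timing of the events. The change adds no earlier warning within a completed six-patient cohort, where both thresholds are crossed by the second patient.
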